### **5.1.6 Safety assessments**

#### **5.1.6.1 Laboratory safety assessments**

Blood and urine samples for determination of clinical chemistry, haematology, and urinalysis will be taken at visits in accordance with the schedule outlined in [Table 1](#). Haematology, Clinical chemistry, and Urinalysis samples should be collected at unscheduled visits for assessing an asthma exacerbation, at a minimum. Other unscheduled visits may be initiated as needed, and assessments performed as per investigator’s judgement. For dosing visits, all samples will be taken prior to the administration of IP.

Detailed schedules of the chemistry, haematology, and urinalysis tests are presented in [Table 2](#), [Table 3](#), [Table 4](#), and [Table 5](#), respectively.

**Table 2 List of safety laboratory tests**

| Haematology/Haemostasis (whole blood)    | Clinical Chemistry (serum)     |
|---|---------------------------------------|
| B-Haemoglobin (Hb)                              | S-Alkaline phosphatase (ALP)          |
| B-Leukocyte count                               | S-Alanine transaminase (ALT)          |
| B-Leukocyte differential count (absolute count) | S-Aspartate transaminase (AST)        |
| B-Platelet count                                | S-Bilirubin, total                    |
| B-Hematocrit                                    | S-Blood urea nitrogen (BUN)           |
| B-Mean corpuscular volume (MCV)                 | S-Calcium, total                      |
| B-Red blood cell (RBC) count                    | S-Carbon dioxide (CO 2 )   |
|   | S-Chloride                            |
|   | S-Creatinine                          |
|   | S-Creatinine kinase                   |
|   | S-CRP                                 |
| Urinalysis                               | S-Gamma-glutamyl transpeptidase (GGT) |
| U-Nitrite (dipstick)                            | S-Glucose                             |
| U-Bilirubin (dipstick)                          | S-Phosphorus                          |
| U-Glucose (dipstick)                            | S-Potassium                           |
| U-Blood (dipstick)                              | S-Sodium                              |
| U-Protein (dipstick)                            | S-Total cholesterol                   |
| U-Ketones (dipstick)                            | S-Uric acid                           |
| Urine microscopy and urine casts (as required)  |                                       |
| Urine culture (as required)                     |                                       |

**Table 3 Clinical Chemistry (serum) Tests schedule**

| Visit   | V1 | V3
(Rand) | V5 | V7 | V16 | V23 | V29          | IPD
Visit | UNS
Visit |
|----------------|-----------|----------------------|-----------|-----------|------------|------------|---------------------|----------------------|----------------------|
| Week    | -6 | 0             | 4  | 8  | 26  | 40  | 52
(EOT) | N/A           | N/A           |
| ALP            | X         | X                    | X         | X         | X          | X          | X                   | X                    | X                    |
| ALT            | X         | X                    | X         | X         | X          | X          | X                   | X                    | X                    |
| AST            | X         | X                    | X         | X         | X          | X          | X                   | X                    | X                    |
| BUN            | X         | X                    | X         | X         | X          | X          | X                   | X                    | X                    |
| Calcium, total |           | X                    |           |           |            |            | X                   | X                    | X                    |

| Visit         | V1 | V3
(Rand) | V5 | V7 | V16 | V23 | V29                | IPD
Visit | UNS
Visit |
|----------------------|-----------|----------------------------|-----------|-----------|------------|------------|---------------------------|----------------------------|----------------------------|
| Week          | -6 | 0                   | 4  | 8  | 26  | 40  | 52
(EOT) | N/A                 | N/A                 |
| Chloride             |           | X                          |           |           |            |            | X                         | X                          | X                          |
| CO 2      |           | X                          |           |           |            |            | X                         | X                          | X                          |
| Creatinine           | X         | X                          | X         | X         | X          | X          | X                         | X                          | X                          |
| Creatinine
kinase |           | X                          |           |           |            |            |                           |                            |                            |
| CRP                  |           | X                          |           |           |            |            |                           |                            |                            |
| GGT                  | X         | X                          | X         | X         | X          | X          | X                         | X                          | X                          |
| Glucose              |           | X                          |           |           |            |            | X                         | X                          | X                          |
| Phosphorus           |           | X                          |           |           |            |            | X                         | X                          | X                          |
| Potassium            |           | X                          |           |           |            |            | X                         | X                          | X                          |
| Sodium               |           | X                          |           |           |            |            | X                         | X                          | X                          |
| Total bilirubin      | X         | X                          | X         | X         | X          | X          | X                         | X                          | X                          |
| Total cholesterol    |           | X                          |           |           |            |            | X                         | X                          | X                          |
| Uric acid            |           | X                          |           |           |            |            | X                         | X                          | X                          |

**Table 4 Haematology/Haemostasis (whole blood) schedule**

| VISIT   | V1        | V3       | V4       | V5       | V7       | V9        | V11       | V13       | V15       | V17       | V19       | V21       | V23       | V25       | V27       | V29       | V30       | V31       | IPD Visit  | UNS Visit  |
|---|-----------|----------|----------|----------|----------|-----------|-----------|-----------|-----------|-----------|-----------|-----------|-----------|-----------|-----------|-----------|-----------|-----------|------------|------------|
|   |           |          |          |          |          |           |           |           |           |           |           |           |           |           |           | (EOT)     | (FU)      | (FU)      |            |            |
| Week                                     | -6 | 0 | 2 | 4 | 8 | 12 | 16 | 20 | 24 | 28 | 32 | 36 | 40 | 44 | 48 | 52 | 56 | 72 | N/A | N/A |
|   |           |          |          |          |          |           |           |           |           |           |           |           |           |           |           |           |           |           |            |            |
| B-Haemoglobin                                   | X         | X        | X        | X        | X        | X         | X         | X         | X         | X         | X         | X         | X         | X         | X         | X         | X         | X         | X          | X          |
| B-Leukocyte count                               | X         | X        | X        | X        | X        | X         | X         | X         | X         | X         | X         | X         | X         | X         | X         | X         | X         | X         | X          | X          |
| B-Leukocyte differential count (absolute count) | X         | X        | X        | X        | X        | X         | X         | X         | X         | X         | X         | X         | X         | X         | X         | X         | X         | X         | X          | X          |
| B-Platelet count                                | X         | X        | X        | X        | X        | X         | X         | X         | X         | X         | X         | X         | X         | X         | X         | X         | X         | X         | X          | X          |
| B-Hematocrit                                    | X         | X        | X        | X        | X        | X         | X         | X         | X         | X         | X         | X         | X         | X         | X         | X         | X         | X         | X          | X          |
| B-Mean corpuscular volume                       | X         | X        | X        | X        | X        | X         | X         | X         | X         | X         | X         | X         | X         | X         | X         | X         | X         | X         | X          | X          |
| B-Red blood cell count                          | X         | X        | X        | X        | X        | X         | X         | X         | X         | X         | X         | X         | X         | X         | X         | X         | X         | X         | X          | X          |

**Table 5** Urinalysis schedule

| VISIT   | V
1 | V3
(Rand) | V
5 | V7 | V16 | V23 | V29         | IPD
Visit | UNS
Visit |
|---|--------|--------------|--------|----|-----|-----|-------------|--------------|--------------|
| Week  | -6     | 0            | 4      | 8  | 26  | 40  | 52
(EOT) | N/A          | N/A          |
| U-Nitrite (dipstick)                            | X      | X            | X      | X  | X   | X   | X           | X            | X            |
| U-Bilirubin (dipstick)                          | X      | X            | X      | X  | X   | X   | X           | X            | X            |
| U-Glucose (dipstick)                            | X      | X            | X      | X  | X   | X   | X           | X            | X            |
| U-Blood (dipstick)                              | X      | X            | X      | X  | X   | X   | X           | X            | X            |
| U-Protein (dipstick)                            | X      | X            | X      | X  | X   | X   | X           | X            | X            |
| U-Ketones (dipstick)                            | X      | X            | X      | X  | X   | X   | X           | X            | X            |
| Urine microscopy and urine casts (as required)* |        |              |        |    |     |     |             |              |              |
| Urine culture (as required)*                    |        |              |        |    |     |     |             |              |              |

\* Urine samples will be analysed locally and sent for analysis at the central lab only when a positive dipstick result for any parameter is observed.

The total volume of blood that will be collected from each subject during the study is presented in [Table 6](#).

**Table 6** Volume of blood to be drawn from each subject

| Assessment                     |                               | Sample volume (mL) | No. of samples | Total volume  (mL) |
|--------------------------------|-------------------------------|--------------------|----------------|--------------------------------|
| Safety                         | Clinical chemistry            | 2.5                | 7              | 17.5                           |
|                                | Haematology (including HbA1c) | 2                  | 18             | 36                             |
| FSH, $\beta$ -HCG  |                               | 1                  | 1              | 1                              |
| Serology                       |                               | 7.5                | 1              | 7.5                            |
| IgE                            |                               | 2.5                | 3              | 7.5                            |
| Phadiatop ®         |                               | 2.5                | 1              | 2.5                            |
| Periostin                      |                               | 6                  | 5              | 30                             |
| DPP4 and other biomarkers      |                               | 10                 | 5              | 50                             |
| ADA/nAb                        |                               | 3.5                | 5              | 17.5                           |
| PK                             |                               | 3.5                | 6              | 21                             |
| Pharmacogenetics   |                               | 10                 | 1              | 10                             |
| Total                   |                               |                    |                | 200                     |

 Female subjects only

 Optional

 The number of samples may be changed due to additional sampling at unscheduled visits, and the blood volume required may be altered to fit the assay requirements. The total volume of blood drawn from each patient over the course of the study will not exceed 450 mL.

Urine will be tested locally and sent for analysis at the central lab only when a positive dipstick result for any parameter is observed. Blood samples for determination of haematology/haemostasis and clinical chemistry will be performed at a central laboratory. For information on methods of collection, assessment, labelling, storage and shipment of samples please refer to the separate Laboratory Manual.

A copy of the laboratory result report should be signed and dated by the Investigator and retained at the study site.

The Investigator should make an assessment of the available results with regard to clinically relevant abnormalities. The laboratory results report should be signed and dated, and retained at site as source data for laboratory variables. For information on how AEs based on laboratory tests should be recorded and reported, see [Section 6.3](#).

**NB.** In case a subject shows an AST or ALT  $\geq 3 \times \text{ULN}$  or total bilirubin  $\geq 2 \times \text{ULN}$  please refer to Appendix E, ‘Actions required in cases of combined increase of Aminotransferase and Total Bilirubin – Hy’s Law’, for further instructions.

### 5.1.6.2 Pregnancy Test

The following tests are applicable to female subjects only, and will be conducted in accordance with the schedule provided in [Table 1](#)

- Serum  $\beta$ -human chorionic gonadotropin ( $\beta$ -HCG) – the test done at enrolment (Visit 1) only, for WOCBP and adolescent females (analyzed at central laboratory)
- FSH – the test done at enrolment (Visit 1) only, for female subjects to confirm postmenopausal status in women <50 years who have been amenorrheic for >12 months
- Urine HCG – the test will be performed at the study site for WOCBP and adolescent females at each treatment visit before IP administration using a dipstick. Positive urine test result must be confirmed with serum  $\beta$ -HCG.

### 5.1.7 Physical examination

Physical examinations (complete and brief) will be performed in accordance with schedule provided in [Table 1](#).

Baseline data will be collected at Visit 1. Any new finding(s) or aggravated existing finding(s), judged as clinically significant by the Investigator, will be reported as an AE as described in section [6.1](#).

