## 4.1 Enrolment/run-in period

### 4.1.1 Enrolment (Visit 1)

Each potential subject who is at, or over the age of majority (as per local law) will provide informed consent prior to the start of any study specific procedures and undergo assessments applicable for this visit (see [Table 1](#)).

For subjects less than the age of majority, in addition to the subject providing informed assent, the subject's legal guardian must also provide their informed consent.

With the exception of documentation of informed consent and assent (if applicable), which can be completed up to 30 days prior to Visit 1, all other Visit 1 procedures should be completed within a 1 to 3-working day window. The 3-day window is to enable subjects to return if necessary for the spirometry assessments on a morning when they have had their BD medications withheld in accordance with the spirometry instructions (see section [5.1.2](#)). The registration of the subject's enrollment via IWRS/IVRS should occur on the day when the Visit 1 procedures are performed.

Visit 1 assessments are primarily concerned with assessing the subject's eligibility (inclusion/exclusion) criteria, including their asthma disease state, the requisite level of severity based on maintenance medications, exacerbation history, and the current level of control based on an initial ACQ-6 score.

Spirometry will also be performed at Visit 1. Subjects must have a pre-BD FEV1 value <80% of their PNV (<90% for subjects 12 to 17 years of age) in order to proceed in the study (as per Section [3.1](#), criterion [8](#)). If not, the subject will be screen failed.

Other study assessments and procedures to be performed at this visit include the recording of the subject's demographics, a complete physical examination (including height and weight), vital signs, a dECG, recording the subject's medical/surgical history and concomitant medications, collection of blood samples for haematology/clinical chemistry, serology and biomarkers, collection of a urine sample for urinalysis, and a pregnancy test for WOCBP.

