## **4.2 Treatment period**

Inclusion criteria at randomization will be confirmed at Visit 3. Before randomization the subject's compliance with their usual asthma controller ICS-LABA and other asthma controller medication, and ePRO completion must be confirmed (see section [3.1](#), inclusion criteria [18](#) and [19](#)).

Subjects confirmed as eligible will be randomized at Visit 3 (Week 0) in a 1:1 ratio (i.e. 385 subjects on tralokinumab, and 385 subjects on placebo). Subjects will be administered tralokinumab 300mg or placebo via subcutaneous injection at the study site Q2W for a total of 26 doses.

The first dose of the IP will be administered following randomization through IWRS/IVRS at Visit 3.

Following randomization the subject will receive 52 weeks of double-blind treatment, with the last dose of tralokinumab/placebo administered at Visit 28 (Week 50).

Subjects will have scheduled visits at 2-week intervals to complete protocol-specific assessments and IP administration, as listed in [Table 1](#). Restrictions as set out in section [7.7.2](#) will continue to apply throughout the treatment period. In case of an asthma worsening/exacerbation (see section [5.1.1](#)), subjects should be evaluated at the study site,

when feasible, at an unscheduled visit, or ordinary visit if the worsening happens to fall within a scheduled visit window.

Subjects will continue to measure their PEF at home, as well as record asthma symptoms and responses to questionnaires in the Asthma Daily Diary throughout the 52-week treatment period (see section 5.2.2 for details).

Subjects will have brief physical exams performed at times listed in Table 1. A complete physical exam will be performed at Visit 29 (Week 52).

Additional blood samples will be obtained from the subjects at Visits 3, 9, 16 and 29 to further explore the relationship between the clinical response of tralokinumab and biomarkers.

The subject's adherence for completing all questionnaires in the ePRO will be assessed at all visits during the treatment period, with retraining provided as required.

At Week 52 subjects will come to the site for the End of Treatment (EOT) visit. The subject should bring the ePRO device to the EOT visit and complete the ACQ-6, AQLQ(S)+12, EQ-5D-5L, and the WPAI + CIQ, unless they have been completed at home prior to the visit.

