## **8.4 Outcome measures for analyses**

### **8.4.1 General Definitions**

#### **8.4.1.1 Definition of baseline and subject baseline variables**

For spirometry variables the measurement recorded at the baseline visit (Visit 3) will be used as baseline. If the Visit 3 measurement is missing, the last non-missing value before Visit 3 will be used as baseline instead. For post-BD FEV1, the measurement after the first BD administration is the baseline.

The baseline for the ePRO variables (ACQ-6, AQLQ(s)+12, WPAI-CIQ, and EQ-5D-5L) will be captured on the ePRO device at Visit 3. Baseline for Asthma Daily Diary variables will be the bi-weekly mean for data collected between study day -14 and -1 (i.e. 14 to 1 day before Visit 3).

For laboratory data and physical examination, baseline will be defined as the latest non-missing assessment prior to first dose.

Absolute change from baseline outcome variables is computed as (post-randomization value – baseline value).

Percent change from baseline is computed as  $((\text{post-randomization value} - \text{baseline value}) / \text{baseline value}) \times 100\%$ . If either the post-randomization value or the baseline value is missing, then the absolute or percent change from baseline value will also be set to missing.

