#### 8.4.4 Calculation or derivation of safety variable(s)

The following safety data will be collected: vital signs, physical examination, 12-lead dECG, hematology, clinical chemistry, urinalysis, and reported AEs.

Change from baseline (Visit 3) to each post-baseline time point where scheduled assessments were made will be calculated for relevant measurements.

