#### 8.4.4.5 Physical examination

Complete and brief physical examinations will be performed at time points specified in [Table 1](#). What is included in the assessment will be dependent on whether the examination is complete or brief, as described in [Section 5.1.7](#). For the brief physical examination, only information on whether the assessment was performed or not will be recorded.

Each component of the baseline visit (i.e., Visit 3) complete physical examination will be recorded as normal or abnormal. Each component of the follow-up complete physical examinations will be recorded as normal, same as baseline, or new/aggravated.

Any new finding(s), or aggravated existing finding(s), judged as clinically significant by the Investigator, will be reported as an AE.

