#### **8.5.8.4 Physical Examination**

Shift tables (normal, abnormal) of baseline versus EOT will be generated, presenting the assessment for each component of the complete physical examination separately.

Listings of abnormal results will be produced.

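### The physical examination baseline is Visit 1 in Section 5.1.7 but Visit 3 in Sections 8.4.4 and 8.4.4.5, and the planned shift table cannot show worsening of a component already abnormal at baseline

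*Protocol*

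**What the plan says.** Section 5.1.7, in the assessment part of the protocol, states "Baseline data will be collected at Visit 1". Its next sentence requires new or aggravated findings to be reported as AEs if the investigator considers them clinically significant.

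The statistical part points elsewhere:

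- Section 8.4.4.5: "Each component of the baseline visit (i.e., Visit 3) complete physical examination will be recorded as normal or abnormal".
- Section 8.4.4, for safety variables in general: "Change from baseline (Visit 3) to each post-baseline time point where scheduled assessments were made will be calculated for relevant measurements".
- Section 8.4.1.1: "For laboratory data and physical examination, baseline will be defined as the latest non-missing assessment prior to first dose".

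Table 1 schedules a complete examination at Visit 1, at Visit 3 and at Week 52 (Visit 29, EOT).

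For the record after dosing, Section 8.4.4.5 says "Each component of the follow-up complete physical examinations will be recorded as normal, same as baseline, or new/aggravated". For the summary, Section 8.5.8.4 says "Shift tables (normal, abnormal) of baseline versus EOT will be generated", component by component, and adds a listing of abnormal results.

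**The concern.** The follow-up record is a comparison made at the site, not a free-standing finding. 'Same as baseline' and 'new/aggravated' mean something only once the reference visit is known. The section that describes how the examination is done points to Visit 1, while the section that defines the recorded categories points to Visit 3. The AE rule for examination findings in Section 6.3.6 also compares with a baseline assessment and names no visit.

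The table is a second, separate matter. The form collects whether an abnormality is unchanged or worse, and the planned table then drops that distinction for components abnormal at baseline.

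Physical examination is a named safety outcome (Section 2.3). At stake is whether its one planned table can be read as a description of change on treatment.

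**Working it through.** No figure in the plan is involved, so the check sets the passages side by side and enumerates the cases.

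**1. When does the choice of reference visit change the record?** Take one component that is abnormal at Week 52.

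| Visit 1 | Visit 3 | Week 52 | Recorded against Visit 1 | Recorded against Visit 3 |
|---|---|---|---|---|
| normal | normal | abnormal | new/aggravated | new/aggravated |
| abnormal | abnormal, unchanged | abnormal, unchanged | same as baseline | same as baseline |
| normal | abnormal | abnormal, as at Visit 3 | new/aggravated | same as baseline |
| abnormal | normal | abnormal, as at Visit 1 | same as baseline | new/aggravated |

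The two readings agree when nothing changed in run-in. They disagree in the last two rows, where the finding appeared or resolved between Visit 1 and Visit 3.

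**2. Does Section 8.4.1.1 settle it?** For the analysis, largely yes: the last pre-dose examination is Visit 3 if it was done, and Visit 1 otherwise. That agrees with Sections 8.4.4 and 8.4.4.5. It does not fully settle the recorded category. A site that compared with Visit 1 has already written 'same as baseline' or 'new/aggravated' on that footing, and an analysis rule applied later cannot fully undo it. 'Same as baseline' can also be turned into normal or abnormal for the shift table only if the visit it refers to is known.

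**3. What does the shift table keep?** There are 2 baseline states and 3 follow-up categories, so 2 × 3 = 6 combinations go into a 2 × 2 table.

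| Baseline | Follow-up record | Cell in the shift table |
|---|---|---|
| normal | normal | normal to normal |
| normal | same as baseline | normal to normal |
| normal | new/aggravated | normal to abnormal |
| abnormal | normal | abnormal to normal |
| abnormal | same as baseline | abnormal to abnormal |
| abnormal | new/aggravated | abnormal to abnormal |

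The first two rows describe the same state, so merging them loses nothing. The last two describe different states and share a cell. A new abnormality in a component that was normal remains visible. Worsening of one already abnormal does not.

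**4. Where else would worsening appear?** Brief examinations record only whether they were done (Sections 5.1.7.2 and 8.4.4.5). Week 52 is therefore the one scheduled visit after first dose with component-level findings, apart from any discontinuation or unscheduled examination. A worsened abnormality would still be in the listing under Section 8.5.8.4 and, if clinically significant, among the AEs.

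**The case against.** The strongest reply is that the analysis baseline is not in dispute. Three statements in Section 8 lead to Visit 3, and Section 5.1.7 defines no analysis variable. The categories 'same as baseline' and 'new/aggravated' appear as recorded values only in Section 8.4.4.5, directly after the sentence naming Visit 3, so that section can be read as the recording rule. Visit 1 in Section 5.1.7 may serve another purpose. AEs are collected from consent (Section 6.3.1) and assigned to periods by onset date (Section 8.4.4.1), so a finding that arises in run-in can be a run-in AE and also part of the pre-dose baseline. On the table, the reply is that layout is largely a matter of preference, that more tables are not excluded, and that the listing and AE reports remain.

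Much of this stands. It rules out three stronger readings that a reader might infer:

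- *The analysis has no defined baseline.* Section 8.4.1.1 gives one.
- *Findings have been misclassified.* The documents do not show which visit sites used, and the eCRF instructions are not available.
- *Aggravated findings are lost to safety reporting.* The limitation is in the shift table alone, and only for components abnormal at baseline.

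The reply does not remove the conflict. Section 5.1.7 is where a site would look for how to do the examination, and its Visit 1 sentence stands next to the AE rule for new or aggravated findings. A literal reading is reasonable, because Section 8.4.4.4 does make Visit 1 the baseline for the digital ECG. Nor does it answer the table point: Section 8.5.8.4 itself fixes the two categories, while Section 8.4.4.5 collects three.

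**Conclusion.** Both parts hold in limited form. The protocol gives conflicting statements of the examination baseline. This leaves the relative follow-up categories ambiguous for subjects whose findings changed between Visit 1 and Visit 3. The shift table cannot separate a worsened from an unchanged abnormality in a component abnormal at baseline.

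The importance is minor. The data are descriptive safety data, and no efficacy test depends on them. The documents give neither the number of subjects whose examination changed in run-in nor the number with an abnormal component at baseline, so the size cannot be stated. Under blinding one would expect similar effects in both arms, but that is an expectation and not something the documents show. The conclusion assumes that no eCRF instruction already names the reference visit; if one does, the first part reduces to correcting the wording of Section 5.1.7.

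**What to change.** **Section 5.1.7.** Reconcile it with Sections 8.4.1.1 and 8.4.4.5. State that the last examination before first dose, normally Visit 3, is the reference for the post-dose categories 'same as baseline' and 'new/aggravated', and that Visit 1 remains the reference for findings that arise during run-in. Making Visit 3 the only reference would leave run-in findings with nothing to be compared with, although AEs are collected from consent.

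**Section 8.5.8.4.** Tabulate baseline (normal, abnormal) against the recorded EOT categories (normal, same as baseline, new/aggravated).

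**Examinations already recorded.** This edition is dated 9 June 2017 and Section 9.3 expects the study to end by Q3 2017, so many Week 52 examinations have presumably been done. A change of wording cannot reach those. The sponsor should document which visit sites were instructed to use as the reference and note it with the table.

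The cost is a sentence or two in each section and one changed table shell. The categories are already collected.
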